9.4 Recording and reporting of SAEs, SARs AND SUSARs

All SAEs occurring from the time of written informed consent/ randomisation until 12 months post randomisation should be recorded on the SAE Report Form. Trial centres will use a standardised electronic SAE form to inform the Trial Manager of SAEs. All SAEs (other than those defined in this protocol as not requiring reporting) must be reported on the SAE reporting form on REDCAP .

The Trial Management Team will perform an initial check of the report and request any additional information from the site team. SAEs will also be reviewed at TMG meetings. DSMC and TSC will get a list of SAEs.

The 'causality', 'expectedness' and 'seriousness' of SAEs (i.e. relationship to trial treatment) will be assessed by the local investigator(s) on the SAE form. A clinician unrelated to surgery may be consulted on the SAE assessment. All SAEs, will be reviewed by the DISCUS Trial Manager and discussed with Chief Investigators to determine whether the SAE is "*related*" and "*unexpected*" as defined by the HRA guidance. These will then be assessed by the DISCUS Nominated Person.

The assessment of 'causality' by the local investigator will not be downgraded by the DISCUS Trial Office, even if the Nominated Person does not concur with the assessment. Under these circumstances both assessments will be recorded and causality deemed as 'related'.

For SAEs that require reporting, expectedness of SARs will be performed centrally by the Nominated Person for the trial and determined according to the Sponsor-.

The DISCUS Trial Office is responsible for reporting SAEs, where appropriate, to the Sponsor and REC within required timelines. An SAE occurring to a participant will be reported to the REC that gave a favourable opinion of the study where in the opinion of the Chief Investigators the event was 'related' (resulted from administration of any of the research procedures) and 'unexpected' in relation to those procedures.

All SUSARs (Suspected and Unexpected Serious Adverse Reaction – a serious adverse reaction, the nature and severity of which is not consistent with the information documented about the procedure or treatment in question) will be reported by the DISCUS Trial office to the relevant Competent Authority and other parties as applicable. For fatal and life-threatening SUSARs, this will be done no later than seven calendar days after the Sponsor or delegate (i.e. CTU) is first aware of the reaction. Any additional relevant information will be reported within eight calendar days of the initial report. All other SUSARs will be reported within 15 calendar days.

For each **SAEs/SUSARs** the following information will be collected:

- a) full details in medical terms and case description
- b) event duration (start and end dates, if applicable)
- c) action taken
- d) outcome
- e) seriousness criteria
- f) causality (i.e. relatedness to trial treatment), in the opinion of the investigator

Any change of condition or other follow-up information should be emailed to the Sponsor as soon as it is available or at least within 24 hours of the information becoming available. Events will be followed up until the event has resolved or a final outcome has been reached." OCTRU safety reporting procedures will be followed at all times.

Management in the event of withdrawal

Each participant has the right to withdraw from the study at any time. In addition, the Investigator may discontinue a participant from the study, at any time, if they consider it necessary for any reason.

Participants in DISCUS may be withdrawn from treatment if:

1. Following consent, but prior to surgery, a patient clinically deteriorates such that surgery is no longer considered in the patient's best interests.
2. Following consent, but prior to surgery, surgery is postponed beyond the 72-hour window.
3. During surgery, where the surgeon considers use of duroplasty is not appropriate or possible.

Where a participant withdraws from treatment they will continue to be followed-up unless they also withdraw from follow-up. Participants may be withdrawn from follow-up for the following reasons, if the participant has not received treatment by the time of withdrawal takes place for this reason then they will also be withdrawn from treatment:

4. During surgery, where the surgeon discovers that the dura is substantially damaged by the penetrating injury (e.g., stab injury)
5. A patient declines to continue participation in the trial.

Participants that withdraw from follow-up will be asked whether the data acquired up to the point of withdrawal can be retained. The reason for withdrawal will be recorded in the participant's medical records and in the DISCUS Withdrawal Case Report Form (CRF). If the participant is withdrawn due to a SAE, the local investigator will arrange for follow-up visits until the SAE has resolved or stabilised.

Members of the trial team will explain to participants the value of continuing to complete questionnaires and participate in assessments at follow-up. Where possible, participants who have withdrawn from the trial intervention should continue to be followed up, unless they withdraw consent for this.

9.5 Responsibilities

Principal Investigator (PI):

Checking for SAE's when participants attend for treatment / follow-up.

- Using medical judgement in assigning seriousness and causality and providing an opinion on whether the event/reaction was anticipated.
- Ensuring that all SAEs are recorded and reported to the sponsor within 24 hours of becoming aware of the event and provide further follow-up information as soon as available. Ensuring that SAEs are chased with Sponsor if a record of receipt is not received within 2 working days of initial reporting.
- Ensuring that SAEs are recorded and reported to the sponsor in line with the requirements of the protocol.

Chief Investigator (CI) / delegate or independent clinical reviewer:

1. Clinical oversight of the safety of patients participating in the trial, including an ongoing review of the risk / benefit.
2. Using medical judgement in assigning the SAEs seriousness, causality and whether the event was anticipated where it has not been possible to obtain local medical assessment.
3. Using medical judgement in assigning whether and event/reaction was anticipated or expectedness.
4. Immediate review of all SUSARs.
5. Review of specific SAEs in accordance with the trial risk assessment and protocol as detailed in the Trial Monitoring Plan.
6. Assigning Medical Dictionary for Regulatory Activities (MedDRA) or Body System coding to all SAEs

Sponsor: (NB where relevant these can be delegated to CI)

7. Central data collection and verification of SAEs and SUSARs according to the trial protocol onto a database.
8. Reporting safety information to the CI, delegate or independent clinical reviewer for the ongoing assessment of the risk / benefit according to the Trial Monitoring Plan.
9. Reporting safety information to the independent oversight committees identified for the trial (Data Safety and Monitoring Committee (DSMC) and / or Trial Steering Committee (TSC)) according to the Trial Monitoring Plan.
10. Expedited reporting of SUSARs to the REC within required timelines.
11. Notifying Investigators of SUSARs that occur within the trial.
12. The unblinding of an assessor for the purpose of expedited SUSAR reporting [For double blind trials only].

Trial Steering Committee (TSC):

In accordance with the TSC charter (filed in the trial eTMF), periodically reviewing safety data and liaising with the DSMC regarding safety issues.

Data Safety Monitoring Committee (DSMC):

In accordance with the DSMC charter (filed in the trial eTMF), periodically reviewing overall safety data to determine patterns and trends of events, or to identify safety issues, which would not be apparent on an individual case basis.

10 STATISTICS AND DATA ANALYSIS

10.1 Sample size calculation

The sample size is based on the primary outcome of change in AMS score from baseline to 6 months. Assuming a 6-month improvement in Δ AMS from a mean(SD) of 17(25) in the control arm to 28(25) in the intervention arm, allowing for 15 % patient loss to follow-up by 6 months (including patient death which is estimated to be around 2-3 % by 6 months), a total sample size of 222 patients is required with statistical power of 85 % and 2-sided significance level of 5 %. The assumed difference in Δ AMS and SD are based on our exploratory study [Phang et al., 2015] and are supported by data from the EMSCI database and other published series [Fehlings et al., 2016; WU et al., 2015] in which Δ AMS is between 15 – 18 with SD ranging from 15 – 25. There is expected correlation between the baseline and 6-month AMS scores, however there is no robust data on the strength of the correlation for patients with severe TSCI and thus we are unable to accurately account for this in the sample size calculation. By assuming no correlation, with the expectation that correlation is observed in the data, statistical power to detect a difference between the two treatment arms will be increased.

The threshold difference in Δ AMS between the two trial arms of 11 points is comparable to other RCTs for cervical TSCI, for example the RISCIS study was powered to detect a 9-point difference between treatment arms [Fehlings et al., 2016]. The minimal clinically important difference in AMS remains controversial and there is no clear consensus amongst the clinical community [Wu et al., 2015]. This is mainly because the segmental distribution of any increased AMS score is functionally more important than the absolute value of the change, e.g. a Δ AMS in hand muscles is functionally more important than the same change distributed over many muscle groups. Based on our discussions with patients and international experts, for a low cost, low risk treatment such as duroplasty, any improvement in motor function would be considered beneficial. We will use functional scales as secondary outcomes including CUE-Q (hand function), grip strength, WISCI II (walking) and SCIM III (independence measure that includes sphincter function and validated in TSCI) to confirm that the motor improvement that we seek is associated with functional improvements. In addition, we use a HRQoL scale as a secondary outcome measure (SF-36) aiming to show that the functional improvement translates to improvement in HRQoL.

For a UK-only recruitment, we will maintain statistical power of 85% power, requiring 222 participants. However, as this will be the definitive trial to address the research question, we will aim to increase the statistical power from 85 to 90%, increasing total recruitment from 222 to 260 participants, depending on recruitment rate. Whilst recruitment is in progress, the statistical power will be revised from 85 to 90% if it becomes clear that non-UK centres will secure funding to recruit patients to the study and that the new recruitment figure is achievable within the current recruitment duration. Recruitment progress will be monitored by the TMG and TSC and the final decision to increase recruitment will be made by the TSC.

MECHANISTIC STUDY: Since the proposed mechanistic studies are intended to be hypothesis-generating, no formal sample size calculation has been performed. We consider recruitment of $n \geq 50$ is achievable for UK centres and, if International centres participate, the number is likely to rise. These studies are an important component that will provide information on the mechanism of action of duroplasty. We predict that, compared with bony decompression alone, bony decompression with duroplasty will better decompress the cord (reduce ISP) thus improve cord perfusion (increase SCPP). Improved cord perfusion is predicted to increase cord glucose (and oxygen), which will reduce cord anaerobic metabolism (lower lactate, lower LPR), reduce excitotoxicity (lower glutamate) and reduce cell death (lower glycerol).

All NICUs have the ability to monitor pressure from injured brain (ICP) and the equipment required for ISP monitoring for TSCI is the same. However, only a few NICUs monitor MD. Many NICUs are keen to contribute patients for the RCT, but do not wish to monitor from the injury site. Given these constraints, we elected, following discussions at the Duroplasty meeting in 2018 and in the ICP2019 meeting to have injury site monitoring as an optional extra so not to discourage sites who would otherwise have participated in patient recruitment. Of the injury site monitoring, some units will only do ISP monitoring and others both ISP monitoring and MD monitoring. At St. George's NICU we have a setup for injury site monitoring including ISP [Werndle et al., 2014] and MD [Phang et al., 2015] and Addenbrooke's NICU has a setup for brain. We estimate that St. George's and Cambridge will enter most of their recruited patients into the mechanistic study. Several other units also wish to contribute patients into the mechanistic study (as indicated at the Duroplasty 2018 meeting, the ICP2019 meeting and Table 4); thus, the number of patients recruited into the mechanistic study may exceed 50. We have received letters of interest from 22 centres for ISP monitoring and 15 centres for MD. The consumables have been costed, but any equipment is up to each unit to purchase.

All neurosurgical units have equipment to monitor pressure as it is routinely used for TBI; the same can be used for ISP monitoring. MD equipment is only available in some neurosurgery units. DISCUS

[figure not shown]
will cover costs of consumables (e.g. ISP probes, MD catheters, MD solutions) but will not cover costs of purchasing monitoring equipment.

10.2 Planned recruitment rate

Based on recruiting 222 participants:

- 1) Recruitment starts at month 7 of the project.
- 2) Recruitment at 20 centres.
- 3) Each centre needs 3 months initial approvals period before starting recruitment.
- 4) 4 new centres join per 6 months starting at month 7.
- 5) Mean number of eligible patients per centre per month = 0.84 – 1.07 patients.
- 6) Each centre recruits only 33 % of eligible patients.
- 7) Assumes maximum of 20 recruiting centres

Below is the predicted total no. of (*left*) recruiting centres and (*right*) recruited patients *versus* end of month counted from start of study (85% power).

10.3 Statistical analysis plan

This section provides a brief summary of the statistical analysis with full details being included in a separate statistical analysis plan (SAP). Full details of the statistical analysis will be detailed, in advance of un-blinding of the data, in a pre-specified SAP. The SAP will be written in accordance with the current OCTRU SOPs and will be agreed by the study statistician, the CI and the TMG.

10.3.1 Summary of baseline data and flow of patients

The baseline comparability of the two intervention groups will be considered. The intervention groups will be compared in terms of minimisation factors, demographic characteristics and outcome measures at baseline. Numbers (with percentages) for binary and categorical variables and means (with standard deviations), or medians (with lower and upper quartiles) for continuous variables will be presented; there will be no tests of statistical significance nor confidence intervals for differences between the randomised groups on any baseline variable.

A consort diagram will be produced prior to publication according to the consort statement guidelines.

10.3.2 Primary outcome analysis

The primary analysis will be performed according to the intention-to-treat principle and will be analysed at a 2-sided 5% significance level. The primary outcome, change in AMS score from baseline to 6 months, will be analysed using a generalised estimating equation (GEE) model or mixed model for repeating measures (MMRM) model (depending on the distribution of the primary outcome),

adjusted for randomised treatment and baseline AIS grade. Minimisation factors (age group, country) will be adjusted for as fixed effects. A secondary analysis will be performed adjusting for other important, pre-specified prognostic factors. The mean score and SD will be plotted at each time-point as a visual representation and will be summarised at baseline, 3 months and 6 months.

The AIS ISNCSCI assessment involves systematically completing the AIS form and, therefore, we do not anticipate missing values. Any missing date for the primary outcome (AMS) will be reviewed on a case-by-case basis by an independent clinician who is blinded to the treatment the patient received. AIS grade A or B patients have 0 motor score below the injury by definition and will thus be included in the primary analysis, whereas an AIS grade C patient cannot have missing motor scores and therefore, in the possible but unlikely scenario where values are missing, the AIS will be independently reviewed.

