ISNCSCI requires physical examination of the patient by a competent examiner (such as a physiotherapist) rather than a simple telephone assessment. We will require examiners to provide evidence that they have been trained, e.g. by completing the International Standards Training course (<https://lms4.learnshare.com/dashboard/dash.home.aspx?Z=0itApFGWTBr1Dh0rqKXQPSEwXn9LfMnB173Qk7jP5PM%3d&LSMID=>). The consensus from the patient focus groups is improvement in motor function as assessed by the AMS is a more meaningful outcome to patients in this setting than assessment by a HRQoL questionnaire. Participants in the trial will have the ISNCSCI examination performed on admission before surgery by neurosurgeons at the MTC (prior to randomisation) and at 6 months as part of their routine assessments at the spinal injuries unit by a physiotherapist or rehabilitation doctor. Therefore, the primary outcome measure is within the current standard of care and widely acceptable in the field to both patients and clinicians.

SECONDARY OUTCOMES (NEUROLOGY):

1. Change in AIS sensory score (light touch) at 6 months compared with baseline.
2. Change in AIS sensory score (pin prick) at 6 months compared with baseline.
3. Change in AIS grade at 6 months compared with baseline.

1. – 3. are standardised tools. We will quantify sensation (light touch, pinprick) using standard scales at 6 months versus baseline. The sensory outcomes are part of the ISNCSCI assessment and are conducted by testing and scoring 28 dermatomes on the left and 28 on the right as 0 (no sensation), 1 (reduced sensation) or 2 (normal sensation) giving a total score 0 – 112 for light touch and 0 – 112 for pinprick. From the ISNCSCI assessment, we will derive the AIS grade (A, B, C, D, E) as defined in the Table.

GRADE	DEFINITION	EXPLANATION
A	Complete	No sensory or motor function is preserved in the sacral segments S4-5.
B	Sensory Incomplete	Sensory but not motor function is preserved below the injury level and includes the sacral segments S4-5 (light touch or pin prick at S4-5 or deep anal pressure) AND no motor function is preserved more than three levels below the motor level on either side of the body.

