C	Motor Incomplete	Motor function is preserved at the most caudal sacral segments for voluntary anal contraction OR the patient meets the criteria for sensory incomplete status by light touch, pin prick or deep anal pressure, and has some sparing of motor function more than three levels below the ipsilateral motor level on either side of the body. <50 % of key muscle functions below the level of injury have muscle grade ≥ 3 .
D	Motor Incomplete	Motor incomplete as defined above, with ≥ 50 % of key muscle functions below the neurological level of injury having muscle grade ≥ 3 .
E	Normal	Sensation and motor function graded as normal in all segments.

SECONDARY OUTCOMES (FUNCTION):

4. CUE-Q (to assess upper limb function) at 6 months.
5. Hand grip strength using a dynamometer at 6 months.
6. WISCI-II (to assess walking ability) at 6 months.
7. SCIM-III (to assess self-care and daily living) at 6 months.

SECONDARY OUTCOMES (QUALITY OF LIFE):

8. SF-36 at 6, 12 months.

4. – 8. are standardised tools. We will use these functional scales, which are established in TSCI, to confirm that the motor improvement that we seek is associated with functional improvements: CUE-Q (hand function), grip strength, WISCI II (walking) and SCIM III (independence measure that includes sphincter function and validated in TSCI). In addition, we use one a HRQoL scale as a secondary outcome measure (SF-36,) aiming to show that the functional improvement translates to improvement in HRQoL.

SECONDARY OUTCOMES (SAFETY)

9. Number of re-operations required on the spine within 12 months
10. Total length of hospital stay (Stay in MTC, stay in spinal injury unit, other hospital admissions)
11. Surgical complications and adverse events – recorded postoperatively and at follow-up visits
12. Overall survival (OS) – time from randomisation to death or end of follow-up (1 year)
13. MRI 2 weeks: Size of pseudomeningocele
14. MRI 6 months: Spinal deformity (Cobb angle between superior C2 and inferior C7 endplates); Size of pseudomeningocele,

9. – 12. are objective measures that yield the same value independent of assessor. 14. (spinal deformity) Is a standardised tool. Safety of duroplasty will be assessed in different ways, not only by comparing complications and adverse events, but also by determining the number of re-operations on spine, total hospital stay, OS as well as spinal deformity in the duroplasty versus the non-duroplasty arms.

SECONDARY OUTCOMES (MECHANISM):

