10.7 Procedure(s) to account for missing or spurious data

The number and percentage of individuals with missing data for each outcome at each time point will be summarised by intervention arm, along with reasons for missing-ness if known. The pattern of missing-ness will also be explored and the suitability of missing data assumptions considered.

The main analyses of the primary and secondary outcomes in this trial will be performed using the available case dataset. The impact of missing data on the results of the analysis of the primary outcome at the primary time point will be investigated. Missing data for the primary outcome is expected to be minimal (see 'Primary Outcome Analysis' section).

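### Section 10.3.2 rests inclusion of AIS A/B patients on a zero motor score by definition, which the protocol's own AIS table does not support for grade A and only partly supports for grade B

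*Protocol*

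**What the plan says.** The primary outcome is the change in AMS from baseline to 6 months. Section 3.3 builds the AMS from five myotomes per limb, each rated 0 to 5, for a total of 0 to 100. Section 6.1 admits AIS grades A to C with injuries from C2 to T1.

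The second paragraph of section 10.3.2 deals with missing AMS in three steps:

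- Missing primary outcome data "will be reviewed on a case-by-case basis by an independent clinician who is blinded to the treatment the patient received".
- Then: "AIS grade A or B patients have 0 motor score below the injury by definition and will thus be included in the primary analysis".
- Grade C is set in contrast: such a patient cannot have missing motor scores, so any gap leads to independent review of the AIS.

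Section 10.7 adds: "The main analyses of the primary and secondary outcomes in this trial will be performed using the available case dataset". It refers back to the primary outcome section and describes no substitution of zeros.

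The AIS table in section 3.3 defines the grades as follows:

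- Grade A: "No sensory or motor function is preserved in the sacral segments S4-5".
- Grade B: "Sensory but not motor function is preserved below the injury level and includes the sacral segments S4-5", and in addition "no motor function is preserved more than three levels below the motor level on either side of the body".
- Grade C, by one of its two routes: sensory incomplete status, and the patient "has some sparing of motor function more than three levels below the ipsilateral motor level on either side of the body".

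**The concern.** The sentence on grades A and B gives a definitional fact as the reason for including these patients, in a paragraph about missing values. A zero premise explains inclusion only if it supplies values that were not recorded. So the reader is led to take it as a rule for filling gaps, although the protocol does not say so outright.

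The difficulty is that the fact is not in the protocol's own definitions for grade A, and is there only in part for grade B. In a cervical population the myotomes just below the injury are largely those of the arm and hand, and function there can be real in a patient graded A or B. A zero entered at 6 months would erase it from the endpoint. A zero entered at baseline would overstate the change.

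This matters for the endpoint's meaning more than for its precision. Section 3.1 excludes thoracic injuries partly because the motor score does not register segmental recovery there, so the design relies on cervical segmental recovery being counted. Section 10.1 says that a change "in hand muscles is functionally more important than the same change distributed over many muscle groups". The premise covers two of the three eligible grades.

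**Working it through.** **1. Premise against definitions**

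| Grade | Section 10.3.2 | Table in section 3.3 | Result |
|---|---|---|---|
| A | Motor score 0 below the injury | No function at S4-5; silent on the levels between the injury and S4-5 | Not supported |
| B, first clause | Motor score 0 below the injury | Sensory but no motor function below the injury level | Supported |
| B, second clause | Motor score 0 below the injury | No motor function beyond three levels below the motor level | Looser than the premise |

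For grade B, the second clause would add little if the first already meant zero at every level below the injury. In the grade C row, sparing beyond three levels is a route from sensory incomplete status to grade C. This suggests that sparing within three levels is compatible with grade B. That is tension within the table, not a contradiction of section 10.3.2.

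**2. What the sentence leaves open**

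It does not say whether the zero applies to a single untested myotome or to a whole missing score, at baseline or at 6 months, or by which visit's grade. Scoring one untested myotome as 0 might be seen as deriving the score, which fits section 10.7. Filling a whole missing score is imputation, which does not.

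**3. The plan's own sample size**

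Inputs from section 10.1: mean changes 17 and 28 (difference 11), SD 25, two-sided alpha 5%, power 85%, 15% loss. The two-sample t-test needs 94 per arm (power 85.1%; 93 per arm gives 84.7%). Then 2 × 94 / 0.85 = 221.2, rounded up to 222. The figure reproduces and is not in dispute.

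**4. Illustration of size, on assumed inputs**

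The documents give neither the share of scores that would be filled nor the points lost. Assumptions:

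- Share of analysed patients with a zero-filled 6-month score: 1% to 5% in both arms.
- Mean points erased per affected control patient: 2 to 6. One myotome is worth at most 5.
- Points erased per affected duroplasty patient: the control value × 28/17 = 1.647, giving 3.29 to 9.88. This scaling is also an assumption.

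Analysed patients: 222 × 0.85 = 188.7, or 94.35 per arm. One per cent is 1.9 patients and 5% is 9.4.

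Shift in the difference = share × (duroplasty loss − control loss):

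| Scenario | Shift | Difference | Power (t-test, SD 25, 94.35 per arm) |
|---|---|---|---|
| No filling | 0 | 11 | 85.23% |
| 1%, losses 2 and 3.29 | 0.01 × 1.29 = 0.013 | 10.987 | 85.15% |
| 5%, losses 6 and 9.88 | 0.05 × 3.88 = 0.194 | 10.806 | 84.0% |
| Equal losses in both arms | 0 | 11 | 85.23% |
| Unlikely bound: 5% in the duroplasty arm only, 12 points each | 0.05 × 12 = 0.6 | 10.4 | 81.1% |

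Zeros at baseline would act in the opposite direction on each patient's change.

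**The case against.** The strongest reply has four parts.

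- **Grade B.** The two clauses are joined by a conjunction, and the first already states the premise. A looser second condition does not withdraw the first. This stands: a reader might infer that section 10.3.2 contradicts the grade B definition, but the table supports no more than tension.
- **Zero-filling is inferred.** The protocol says that A/B patients are included; it never says that a blank score is replaced by 0. This also stands. A reader might conclude that the protocol prescribes zero-filling and so contradicts section 10.7 outright. The text does not go that far: blinded review, the A/B statement and the available-case analysis can be read as a sequence, and section 10.3 leaves details to a statistical analysis plan that is not at hand.
- **The route to harm is narrow.** The AIS grade is derived from the same examination. If the 6-month chart is wholly missing, there is no 6-month grade to apply; if the grade is known, most muscles were probably tested. Harm needs a blank myotome with real function that blinded review does not resolve, or a baseline grade carried to 6 months. This limits the size but does not remove the fault.
- **Treating every undocumented muscle as missing is too strict.** One untestable muscle could then discard a whole AMS. This is right, and the fix below lets the blinded reviewer resolve isolated blanks first.

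None of this repairs the premise for grade A. That is a statement the protocol makes about its primary endpoint, not a detail left to a later document.

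**Conclusion.** The point holds in limited form. The justification in section 10.3.2 is unsupported for grade A by the protocol's own table. For grade B it agrees with one clause and sits uneasily with the other. If it is used to enter zeros for unrecorded scores, it can misstate true segmental function at baseline or 6 months, and a whole score filled in this way is not an available case.

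The numerical effect is probably small, because sections 10.3.2 and 10.7 both expect little missing primary outcome data, and it cannot be derived from the documents. On the assumed inputs above, the shift is 0.01 to 0.19 of 11 points with power no lower than 84.0%, and nil if both arms lose equally. A reader might infer a material loss of power from the 81.1% bound. That figure needs filling in one arm only, which is unlikely because section 7.4 blinds the assessors and the missing-data review is blinded too. The sample size of 222 is unaffected.

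**What to change.** In section 10.3.2:

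1. Delete the statement that grades A and B have a zero motor score by definition, and assign no zero from AIS grade alone.
2. Compute the AMS from scores documented on the ISNCSCI chart.
3. Send any blank myotome, for all grades alike, to the blinded independent review already planned.
4. Treat the AMS as missing under section 10.7 only if that review cannot resolve the blank.
5. Keep grade-based zero-filling, if wanted, only as a labelled sensitivity analysis.
6. Reconcile section 10.3.2 with the AIS table in section 3.3 and with section 10.7, so that one rule governs a missing myotome.

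The cost is a change of protocol wording, with no new data or patients. The downside is that a few patients may become formally missing for the primary outcome.
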